6. ASSESSMENT AND FOLLOW-UP

We will identify potential participants by accessing UCLH adolescent diabetes clinic clinic schedule. All patients attending an adolescent diabetes outpatient clinic on a particular day will be invited to participate in the study. Every potential participant will receive an invitation pack with the age appropriate information sheet enclosed by post 1 month before the appointment. Individuals will be invited to express interest via email or by phone, details of both will be provided on the participant information sheet.

The research team will telephone each potential participant 2 weeks before scheduled appointment with their doctor to remind them of their pending appointment, ensure that they have received the invitation pack and answer any questions about the study.

The patient's standard clinician will be able to answer any patient concerns about the study during their standard clinic appointment. We will run interviews on the day of the participant's scheduled appointment at the clinic (approximately 30-60 minutes after standard clinic appointment).

If a potential participant is unable to participate in the interview on the day of the appointment but would like to express his/her views and opinions on the matter, we will offer this participant an interview over the phone at a convenient time. Informed consent to participate in the interview over the phone will be taken in clinic by our researcher.

Prior to the beginning of the phone interview, we will inform the participant that the interview will be audio-recorded and they will be put on loud speaker. We will also let the participant know who is present in the room whilst he/she is being interviewed. We will ask the participant to remain in a quiet room with no relatives/friends present while being interviewed.

Participants will only be interviewed once. We will interview 12-18 participants in total or until theme saturation occurs (Peterson-Sweeney, 2005). Interviews will be held on the day of a participant's clinic appointment within the same hospital to optimise study participation rate and reduce associated travel expenses and time burden.

Interviews will be conducted by a researcher experienced in qualitative studies. The discussion will be held in a quiet room with refreshments provided. Phone interviews will also be conducted in a quiet room with one researcher in the room communicating with a participant. The discussion will take no longer than 30 minutes. Parents will be asked to remain in the waiting area during the study as per NCB Guidelines (NCB Guidelines for Research with Children and Young Adults, 2011).

The researcher will voice a series of prepared statements/questions to promote interview (appendix 1). Written assent/consent will be obtained from study participants and their parents (if present) at the beginning of the discussion or in clinic if phone interview is preferred. The discussion will be audio-recorded.

Audio-recordings from each discussion will be transcribed by [name]. The transcripts will be immediately anonymised. Data analysis will involve a general thematic coding method and will be analysed by two independent researchers (Flick 2009).

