8. REGULATORY ISSUES.....	9
8.1 ETHICS APPROVAL	9
8.2 CONSENT.....	10
8.3 CONFIDENTIALITY	10
8.4 INDEMNITY	10
8.5 SPONSOR	10
8.6 FUNDING.....	10
8.7 AUDITS	10
9. STUDY MANAGEMENT.....	10
10. PUBLICATION POLICY	11
11. REFERENCES	11
Kessels, R. (2003). Patients' memory for medical information. JRSM, 96(5), pp.219-222.	11

GLOSSARY OF ABBREVIATIONS

STUDY SUMMARY

TITLE	Optimising Consultation Summaries to Promote Good Health; Views of Adolescents Attending Diabetes Clinic
DESIGN	Qualitative study involving interviews with young adults face to face and over the phone
AIMS	What are young people's beliefs about the role of consultation summaries and how they can be improved to promote good health
OBJECTIVES	To understand whether consultation letters are being read by the young people To explore their opinions about consultation letter contents and their impact To explore young people's ideas for optimising these letters
POPULATION	12-18 young people aged 12-18 who have been visiting UCLH adolescent diabetes outpatient clinic chosen using purposive sampling
ELIGIBILITY	Adolescents aged 12-18 years attending a diabetes outpatient clinic
DURATION	16 Months. April 2018 – August 2019

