2. STUDY OBJECTIVES

1. To understand whether consultation letters are being read by the young people
2. To explore their opinions about consultation letter contents and their impact
3. To explore young people's ideas for optimising these letters

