8.2 CONSENT

Consent to enter the study must be sought from each participant only after a full explanation has been given, an information leaflet offered and time allowed for consideration. Signed participant consent should be obtained. The right of the participant to refuse to participate without giving reasons must be respected. After the participant has entered the study the clinician remains free to give alternative treatment to that specified in the protocol at any stage if he/she feels it is in the participant's best interest, but the reasons for doing so should be recorded. In these cases, the participants remain within the study for the purposes of follow-up and data analysis. All participants are free to withdraw at any time from the protocol treatment without giving reasons and without prejudicing further treatment.

We will follow NRES guidance on informed consent:

- Young people 16-18: informed consent will be obtained directly from the study participant.
- Young people aged 12-15
 - If parent/carer present, then consent will be obtained from the parent/carer. Assent will be obtained from the study participant.
 - If no parent/carer present, then individual will be assessed for Gillick competence, and if competent, consent will be obtained from the young person.

We will notify participants' General Practitioners of patient recruitment.

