Appendix 1 – Focus group discussion schedule

Tell us a bit about the letters you get

1. Is the letter directed to you, your parent/carer, GP or another doctor?
2. Who reads the letter, you or your parent/carer?
3. Do you show consultation letters to?

Letter content

4. Is the language easy to understand (eg medical terms) What could be better?
5. Does the letter sound friendly or professional to you? How could it be better?
6. Is it too long/short? How could it be better?
7. Does it talk about the right things? How could it be better?

Do these letters help you to improve your health?

8. Are they helpful in any way? (motivate, remind, congratulate, give ideas)
9. Are they unhelpful in any way? (remind of negatives, demoralise, feel sad/worried/angry)
10. What else about your letters could help? Other ideas?

Potential areas of improvement

1. Is there anything that can be improved?
2. Is getting them by post ok? (email/text/postcards better?)

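### Participants hear about the study up to a month before an undated question on who reads the letters, so accounts for Objective 1 may include reading prompted by the study

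*Protocol*

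**What the plan says.** The first objective (Section 2) concerns a behaviour: "To understand whether consultation letters are being read by the young people".

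Section 6 sets out the contacts before the interview. By post: "Every potential participant will receive an invitation pack with the age appropriate information sheet enclosed by post 1 month before the appointment". By phone: "The research team will telephone each potential participant 2 weeks before scheduled appointment with their doctor", in part to "ensure that they have received the invitation pack and answer any questions about the study". The interview then takes place on the day of the appointment, roughly 30-60 minutes after it. For anyone who cannot stay, "we will offer this participant an interview over the phone at a convenient time", with consent taken in clinic beforehand. Each participant is interviewed once.

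The study is titled "Optimising Consultation Summaries to Promote Good Health; Views of Adolescents Attending Diabetes Clinic". Section 8.2 allows consent to be sought "only after a full explanation has been given, an information leaflet offered and time allowed for consideration".

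In Appendix 1, the direct item on reading is item 2: "Who reads the letter, you or your parent/carer". It and its lead-in are in the present tense and refer to letters in general. Section 7 codes responses by what they describe, gives similar responses the same code, and then examines codes on six attributes, of which frequency is one.

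**The concern.** Objective 1 is about what young people ordinarily do with their letters. By the time of the interview they have had about a month in which they may know that the study is about those letters. Someone who usually ignores them has both time and a reason to find one and read it. If the interviewer then asks who reads the letter, without saying when, a truthful answer could describe the habit or the preparation, and the guide does not ask which.

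The phone route raises a second question. A later interview leaves time for the letter from the index visit to arrive, so the two interview modes may refer to different letters.

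What is at stake is the meaning of the Objective 1 findings: whether they describe routine practice or, in part, a reaction to being recruited. Objectives 2 and 3 ask for opinions and ideas and are less exposed, although the phone route could affect which letter the content items bring to mind.

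**Working it through.** The protocol gives no figure to reproduce on this point, so the check sets the passages side by side.

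**1. Timeline, with the appointment as day 0 (Section 6).**

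| Event | Timing |
|---|---|
| Posted pack with information sheet | about 4 weeks before |
| Call from the research team | 2 weeks before |
| Same-day interview | day 0, about 30-60 minutes after the appointment |
| Phone interview | later, at a convenient time |

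The single interview therefore follows the first study contact by about 4 weeks, or longer by phone. No account is taken before the invitation.

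**2. Is the topic known in advance?** Probably. The title names consultation summaries, and a sheet enclosed with an invitation would normally say what the study is about. The sheet is not shown, so this is an inference. Section 8.2 requires a full explanation before consent, but consent is taken in clinic or at the start of the discussion, so that section does not by itself date disclosure to a month ahead.

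**3. Does the guide separate the two kinds of reading?** No. Item 2 names neither a period nor a letter, and nothing else in Appendix 1 asks about reading before or after the invitation.

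**4. Would the analysis separate them?** Only if the participant volunteers the difference. Section 7 would give a separate code to someone who says they looked out a letter because of the study. A person who simply says they read it would share a code with a habitual reader.

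**5. Do the two modes refer to the same letters?** Not necessarily. Within an hour of the appointment, a same-day participant would ordinarily have only earlier letters in mind. A phone participant may have received a newer one. The protocol does not say when letters are issued, so this is possible but not established. Section 4.1 confines recruitment and interviews to August 2018 – April 2019, but no limit is set on the gap between a participant's appointment and the phone interview.

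**6. Can it be repaired afterwards?** Not reliably. There is one interview per person, and Section 6 has transcripts anonymised immediately.

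**The case against.** The strongest reply is that nothing here is an error. Advance notice is part of proper recruitment and consent. The items use the habitual present, which is the ordinary way to ask about routine practice; they do not ask whether the latest letter has been read. They are prompts for a researcher experienced in qualitative work, who may well probe, and the coding rule would separate different answers. All of this stands, and it is why the point is minor. What it does not supply is a prompt that brings out the distinction: the protocol leaves that to the interviewer's initiative or the participant's candour.

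A reader might go further in three ways that the protocol does not support.

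- *Reading will be overstated, by a calculable amount.* With 12-18 interviews, one participant is 1/18 = 5.6% to 1/12 = 8.3% of the sample, and it is tempting to quote that as the shift per prompted reader. But the sample is purposive and may end at theme saturation, no proportion of readers is a planned estimate, and nothing indicates how many participants would be affected. If most letters were read on arrival, before the pack, the effect could be very small.
- *Phone interviews are open-ended and describe a different letter.* The recruitment window bounds them, and the timing of letters is not given. The documents support only that the letters may differ.
- *Tying the questions to the last letter received before the pack solves the problem.* It fixes which letter is discussed, not when it was read, so an older letter dug out because of the study would still count. It also narrows usual practice to a single letter.

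**Conclusion.** The point holds as a modest design weakness. Study contacts about 4 weeks and 2 weeks before the appointment precede an undated reading item, and no prompt separates usual reading from reading done because of the study. Accounts for Objective 1 may therefore include prompted reading, and phone and same-day participants may have different letters in mind.

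This rests on two assumptions: that the information sheet discloses the topic, and, for the phone route, that a letter from the index visit can arrive before the interview. The likely direction is towards more reported reading, since learning of the study gives a reason to read and no evident reason not to. The size cannot be estimated from the protocol. Priority is low.

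**What to change.** Keep the recruitment sequence as it is. In Appendix 1:

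- Keep item 2 as a question about habit, but place it before the study contact, for example: *Before you heard about this study, who usually read your letters?*
- Add one probe: *Have you looked at any clinic letters since hearing about this study, and which ones?*

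In Section 6, state that both questions are used in face-to-face and phone interviews. In Section 7, state that answers to the probe are coded separately from usual reading. Asking which letters were looked at also shows whether a phone participant is drawing on the letter from the index visit.

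The cost is one extra question within the 30-minute limit and some reliance on participants recalling what they did before the invitation. Recruitment and sample size do not change.

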7. DATA ANALYSIS

We will use constant comparative method for the coding process (Krueger and Casey, 2015). The coding process will consist of reading the transcript and analysing responses to statements given by the study participants one by one. We will examine responses to each statement and code each response according to what it describes. If there are several responses to the same statement given, these will be analysed for similarity. If similar, the same code will be given to each, if different, different codes will be given. This coding approach will be maintained for all responses.

In order to avoid analysis errors, transcripts will be coded by two researchers ([name] and [name]) independently and differences agreed. Once the coding process is complete, we will categorize codes and analyse them for frequency, extensiveness, intensity, specificity, internal consistency and participant perception of importance (Krueger and Casey, 2015).

We will share the study outcomes with all participants and their families. We will submit the findings in a peer-reviewed medical journal.

Data and all appropriate documentation will be stored for a minimum of 10 years after the completion of the study, including the follow-up period.

8. REGULATORY ISSUES

8.1 ETHICS APPROVAL

The Study Coordination Centre has obtained approval from the North West Haydock Research Ethics Committee (REC) and Health Regulator Authority (HRA). The study must also receive confirmation of capacity and capability from each participating NHS Trust before accepting participants into the study or any research activity is carried out. The study will be conducted in

accordance with the recommendations for physicians involved in research on human subjects adopted by the 18th World Medical Assembly, Helsinki 1964 and later revisions.

8.2 CONSENT

Consent to enter the study must be sought from each participant only after a full explanation has been given, an information leaflet offered and time allowed for consideration. Signed participant consent should be obtained. The right of the participant to refuse to participate without giving reasons must be respected. After the participant has entered the study the clinician remains free to give alternative treatment to that specified in the protocol at any stage if he/she feels it is in the participant's best interest, but the reasons for doing so should be recorded. In these cases, the participants remain within the study for the purposes of follow-up and data analysis. All participants are free to withdraw at any time from the protocol treatment without giving reasons and without prejudicing further treatment.

We will follow NRES guidance on informed consent:

- Young people 16-18: informed consent will be obtained directly from the study participant.
- Young people aged 12-15
 - If parent/carer present, then consent will be obtained from the parent/carer. Assent will be obtained from the study participant.
 - If no parent/carer present, then individual will be assessed for Gillick competence, and if competent, consent will be obtained from the young person.

We will notify participants' General Practitioners of patient recruitment.

8.3 CONFIDENTIALITY

The Chief Investigator will preserve the confidentiality of participants taking part in the study and is registered under the Data Protection Act.

8.4 INDEMNITY

Imperial College London holds negligent harm and non-negligent harm insurance policies which apply to this study.

8.5 SPONSOR

Imperial College London will act as the main Sponsor for this study. Delegated responsibilities will be assigned to the NHS trusts taking part in this study.

8.6 FUNDING

Funding is not available for this study

8.7 AUDITS

The study may be subject to inspection and audit by Imperial College London under their remit as sponsor and other regulatory bodies to ensure adherence to GCP and the UK Policy Framework for Health and Social Care Research.

9. STUDY MANAGEMENT

The day-to-day management of the study will be co-ordinated through UCLH.

10. PUBLICATION POLICY

The study registration and publication will be supported by The Imperial Open Access Fund and will be available in fully open access journals only.

Appendix 1 – Focus group discussion schedule

Tell us a bit about the letters you get

1. Is the letter directed to you, your parent/carer, GP or another doctor?
2. Who reads the letter, you or your parent/carer?
3. Do you show consultation letters to?

Letter content

4. Is the language easy to understand (eg medical terms) What could be better?
5. Does the letter sound friendly or professional to you? How could it be better?
6. Is it too long/short? How could it be better?
7. Does it talk about the right things? How could it be better?

Do these letters help you to improve your health?

8. Are they helpful in any way? (motivate, remind, congratulate, give ideas)
9. Are they unhelpful in any way? (remind of negatives, demoralise, feel sad/worried/angry)
10. What else about your letters could help? Other ideas?

Potential areas of improvement

1. Is there anything that can be improved?
2. Is getting them by post ok? (email/text/postcards better?)

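### Items 5 and 6 of the Appendix 1 schedule supply words for tone and length before participants use their own, so codes for objective 2 risk echoing the question

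*Protocol*

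**What the plan says.** Objective 2 (Protocol, Section 2) is to explore young people's opinions of what the letters contain and of their impact. The questions that serve it are in Appendix 1. The letter-content block has four items, numbered 4 to 7. Item 5, on tone, reads "Does the letter sound friendly or professional to you? How could it be better". Item 6, on length, reads "Is it too long/short? How could it be better". Item 7 reads "Does it talk about the right things? How could it be better". Item 10, in the next block, asks "What else about your letters could help? Other ideas".

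Section 6 describes how the schedule is used: "The researcher will voice a series of prepared statements/questions to promote interview (appendix 1". It fixes no answer options. Each participant is interviewed once, for at most 30 minutes.

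Section 7 gives the coding rule: "We will examine responses to each statement and code each response according to what it describes". Similar answers to a statement receive the same code and different answers receive different codes. Then "we will categorize codes and analyse them for frequency, extensiveness, intensity, specificity, internal consistency and participant perception of importance".

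In the block on who receives and reads the letters, item 3 is printed as "Do you show consultation letters to", followed by a question mark and with no object.

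**The concern.** In an exploratory interview the participant's own vocabulary is part of the data. Item 5 offers two adjectives as alternatives, although a letter can be both friendly and professional, or neither. Item 6 names two faults and offers no neutral position. In each case the descriptor is in the room before the participant has said anything about tone or length.

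A short answer such as *professional* or *too long* can then be read in two ways: the participant holds that view, or the participant has picked up the nearest available word. The transcript alone may not separate the two. If such answers share a code and the code's frequency is reported, the account of tone and length could owe something to the schedule. At stake is the credibility of those two themes under objective 2. Nothing else in the study is affected.

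**Working it through.** No formula applies and the plan states no figure on this point. The check is a reading of the schedule against the interview and coding plan.

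**1. The four letter-content items.**

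| Item | Topic | Form of the stem | Competing descriptors supplied? | Probe in the same line |
|---|---|---|---|---|
| 4 | Language | Closed, yes/no | No | Asks what could improve |
| 5 | Tone | Either/or | Yes: *friendly*, *professional* | Asks what could improve |
| 6 | Length | Closed | Yes: *too long*, *too short* | Asks what could improve |
| 7 | Topics covered | Closed, yes/no | No | Asks what could improve |

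All four stems are closed, but only items 5 and 6 hand the participant a pair of descriptors. That is 2 of 4.

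**2. The two stems differ.** Item 5 is a true either/or on qualities that do not exclude each other. Item 6 is not: *no* is a natural reply. Its weakness is that both words it names are faults, so the question starts from what may be wrong with the length.

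**3. Does any other item collect an unprompted description of tone or length?**
- The opening heading of the schedule is an open invitation to talk about the letters. The three items under it concern whom the letter is addressed to, who reads it and to whom it is shown.
- The probe attached to items 5 and 6 asks how the letter could be better, after the labels have been given.
- Items 8 and 9 ask whether the letters help or do not help.
- Item 10 and the closing block ask for further ideas, improvements and preferred means of delivery.

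No printed item asks how the letter sounds, or how its length seems, before the interviewer has supplied words for it.

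**4. How wording could reach the codes.** Under Section 7 the unit of coding is the response to a given statement, and similar responses share a code. Suppose several participants answer item 5 with one of its two adjectives and add little. Those answers would be similar, would share a code and would be counted. Independent coding by two researchers guards against error in applying codes. It cannot show whether a word was volunteered or borrowed from the question, because both coders read the same transcript.

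**5. Size.** The protocol gives no data on how participants respond to suggested words, so the extent of any echo cannot be derived. With 12 to 18 participants seen once each, no later interview is planned in which an unprompted view could be recovered.

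**6. Item 3.** This is a separate matter. As printed the sentence stops before its object. The missing words may be absent from the original or may have been lost when the file was read.

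**The case against.** The strongest case on the other side is that these are spoken prompts in a conversation, put by a researcher whom Section 6 describes as experienced in qualitative work. No response set is prescribed. A participant may say *both*, *neither* or something different, and item 6 is easily answered with *no* or *it is fine*. This stands. A reader might infer from the wording that participants face a forced two-way choice; the documents do not support that.

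A reader might also infer that the offered words will become the codes. That does not follow either. Section 7 codes a response by what it describes, not by the words in the question, and frequency is one of six features examined. A bare one-word answer could be given little weight on intensity or specificity. Section 7 does not say how the six features are weighed, however, so this mitigates the risk without removing it.

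The open probes are a fair point too: they carry the participant past a one-word reply. As the check shows, though, they ask for improvements and come after the labels.

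It is tempting to add that adolescents are especially prone to repeat alternatives put to them. The protocol contains nothing on this, and the point does not rest on it.

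Finally, items 5 and 6 contradict no other section and involve no wrong figure. That is correct, and it is why this is a minor suggestion. Item 3 gives no support to the argument about tone and length. Nor can one infer that several interviewers would each complete it differently, since Section 6 speaks of a single researcher putting the questions.

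**Conclusion.** The point holds as a minor wording weakness. Item 5 presents compatible qualities as alternatives, item 6 is a closed stem naming only faults, and no printed item obtains a description of tone or length in the participant's own words beforehand. Given coding by statement and the use of code frequency, there is a risk that the tone and length codes for objective 2 partly echo the interviewer.

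The reach is 2 of the 4 letter-content items; the size within them is unknown. The conclusion assumes that the questions are voiced broadly as printed and that some participants answer briefly. An interviewer who opens neutrally on their own initiative would largely avoid the problem, but the protocol does not ask for this. Item 3 is an editorial matter and counts only if the original is also incomplete.

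**What to change.** In Appendix 1:
- Open item 5 with *How does the letter sound to you?* Keep the present two adjectives as an optional probe, used only after the participant has answered.
- Open item 6 with *What do you think of the length?* Keep the present words as an optional probe in the same way.
- Leave the existing question about improvement at the end of both items.
- Check item 3 against the original. If it is incomplete there as well, finish it, for example *Do you show your letters to anyone? Who?*

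The cost is three lines of the schedule. No item is added, the sample and the coding plan are unchanged, and no extra interview time should be needed. The change is best made before the first interview so that all participants hear the same stems.
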